8.2. SETTING

The study will include patients with congenital HA who have moderate disease ($1\% \le FVIII \le 5\%$), without FVIII inhibitors and severe bleeding phenotype from registries in, but not limited to, the European region. This will provide a broad coverage of a large geographic area, covering different health care settings, and representing a diverse group of patients. Inclusion and exclusion criteria will be applied to select an eligible study population for this study, this will be as subset of the overall patient population in the considered data sources (see section 8.2.6).

The specific registries were determined in a feasibility assessment conducted between April 2023 and October 2023 to identify the most appropriate data sources for this study. A list of the registries that are considered for this study is given below. Actual participation is conditional to contracting.

- UK National Haemophilia Database (UKNHD)
- FranceCoag registry / Reseau FranceCoag

Hemlibra—F. Hoffmann-La Roche Ltd Protocol BO44691, Version 2.0

- HemoNED
- American Thrombosis and Hemostasis Network (ATHN dataset)
- World Bleeding Disorders Registry (WBDR)
- Canadian Bleeding Disorders Registry (CBDR)

Details on the registries considered for this study are provided in section 8.4.

8.2.1. Study Period

The study period will be defined as follows:

- **Start of study period** will be the defined as the date of MA of emicizumab for use among moderate patients without inhibitors in each participating country.
- End of study period will be the last date included in the data extraction across all participating countries (see section 5. For details), anticipated Q4 2030.

8.2.2. Cohort Entry Period

The cohort entry period, when the patients will be assessed in the data source for inclusion in the study, will last from MA of emicizumab for use among moderate patients without inhibitors in each participating country until approximately Q4 2026, to allow for a minimum of 4 year of follow-up until the end of the study period.

This will allow for patients using emicizumab to be included in locations where emicizumab has been approved earlier for use among HA patients with moderate severity, e.g., the US and Canada, before EMA protocol approval. In addition, protocol approval might have occurred after initiation of reimbursement discussion in several locations in Europe. Patients who initiated emicizumab before protocol approval will be considered for inclusion as long as re-consent is not required by the data sources, all other inclusion and exclusion criteria are fulfilled, and no major data enhancement is needed.

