All crude IRs will be presented with 95% CI. For continuous variables, the number of observations, mean, standard deviation, median, lower (1st) and upper (3rd) quartiles, interquartile range (IQR), minimum, maximum, as well as 5th and 95th percentiles will be presented. For categorical variables, the numbers, and percentages of observations for each of the categories will be presented. Numbers and percentages of missing values will be presented.

Milestones

First Data Extraction:

The first data extraction is the date from which the variables used for the analysis as per protocol start to be extracted. The planned first data extraction is approximately 1 year after study launch. The planned first data extraction is Q2 2025.

Last Data Extraction:

The last data extraction is the date after the last included patient has completed their minimum follow-up of 4 years. The planned last data extraction date is Q4 2030.

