8.2.4. Follow-up Period

The study will allow for a minimum of 4 years of follow-up after the index date. The follow-up period will be the time period from index date (first emicizumab initiation) until, **Hemlibra—F. Hoffmann-La Roche Ltd** Protocol BO44691, Version 2.0

the end of the study period (anticipated Q4 2030), a maximum of 5 years of follow-up, or censoring.

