8.4. DATA SOURCES

The data for this study will be collected from existing registries that include haemophilia patients living in the European region and in other countries. A feasibility assessment was performed between April 2023 and October 2023, designed against the EMA guidelines and requirements for registry-based studies (European Medicines Agency, 2021), to inform the selection of the registries for further engagement with the following objectives:

- Provide a general overview of HA disease registries in countries of interest, including details of their objectives, number of contributing sites, and funding sources.
- Assess the potential patient counts of moderate HA patients enrolled in each registry.
- Assess the availability, quality, completeness, frequency, and timeliness of variables required to meet the study requirements.
- Establish operational aspects of data management, including processes for data capture and validation.
- Describe current methods for identification and reporting on AEs, including adverse drug reactions and whether the relatedness to the treatment is reported.
- Identify any potential limitations, confounding factors and biases in the registries, as well as measures taken for mitigation.
- Outline any considerations relating to ethics, data privacy, informed consents, information governance and contracting.

Hemlibra—F. Hoffmann-La Roche Ltd Protocol BO44691, Version 2.0

Description of each of the registers was developed based on information collected from data holders and through desktop research. The full list of registries assessed can be found in Appendix 1. After the feasibility assessment the following registries were considered (listed in Table 7), these registries include a total of 5307 moderate HA patients. Participation of each data source is conditional to contracting.

Data source name	Data Collecti on Period	HA Patient Count	Moderate HA Patient Count	Longitudinal Follow-up	Data lag	Access to Patient- Level Data
UKNHD	1968 – Present	8959	836	YES	Up to 3 months	YES
FranceCoag	2003 – Present	7600	940	YES	Not specified	YES
HemoNED	2015- Present	1431	230	YES	2-3 weeks	YES
ATHNdataset	2020 - Present	100	15	YES	2-6 months	YES
WBDR	2018 – Present	10071	2987	YES	6 months	NO
CBDR	2015 – Present	2799	299	YES	Immediately available	NO

Table 7. Overview of the considered registries.

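### The last extraction leaves no room for registry data lag, so late entrants in lagged registries get about 3.5 recorded years rather than the stated minimum of 4, and person-time has no data-complete end date

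*Protocol*

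**What the plan says.** - **Entry (8.2.2).** The cohort is open "until approximately Q4 2026, to allow for a minimum of 4 year of follow-up until the end of the study period".
- **Follow-up (8.2.4).** "The study will allow for a minimum of 4 years of follow-up after the index date". It runs from the index date to the end of the study period (anticipated Q4 2030), "a maximum of 5 years of follow-up, or censoring".
- **End of study (8.2.1).** "End of study period will be the last date included in the data extraction across all participating countries", again anticipated Q4 2030. This is one date for the whole study.
- **Last extraction (synopsis, Milestones; repeated in 8.1).** "The last data extraction is the date after the last included patient has completed their minimum follow-up of 4 years". Section 5 schedules it for Q4 2030.
- **Data lag (8.4, Table 7).** WBDR 6 months; ATHNdataset 2-6 months; UKNHD up to 3 months; HemoNED 2-3 weeks; CBDR immediately available; FranceCoag not specified.
- **Censoring (8.2.5).** Death, end of observation (with examples) and discontinuation of emicizumab. No date of data completeness is listed.
- **Reports (section 5).** Extractions in Q2 2025 and Q2 2027 feed interim reports in Q4 2025 and Q4 2027, which go into the PSUR/PBRER. The final report is due in Q2 2031.

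The protocol does allow for lag in one place: Assumption 3 in section 8.5.1, on emicizumab uptake. It makes no such allowance in the end of study, the extraction dates or the end of person-time.

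**The concern.** Q4 2026 plus 4 years is Q4 2030, the quarter of the last extraction. An extraction taken then from a registry running 6 months behind is complete only to about Q2 2030. Two things follow.

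First, the 4-year minimum cannot be met in recorded data for the latest entrants in such a registry. The rule for the last extraction has the same gap whatever the calendar date, because it adds nothing for the time needed to record events.

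Second, sections 8.2.1 and 8.2.4 name one study end for all countries. Read literally, a patient with no recorded stop contributes time up to that date, while late events are not yet in the registry. The denominator would then be complete and the numerator not. The primary objective is the incidence of thromboembolic events, so the error would run towards understating the risk, and most strongly in the interim reports, where recent person-time is a large share of the total.

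**Working it through.** **1. The plan's own precision figure.** Section 8.5.2 gives 88% for 200 patients with an average of 4 years (800 person-years, PY), an expected rate of 0.15 and a threshold of 1 per 100 PY.
- Exact upper 95% limit with 2 events: 7.22/800 = 0.90 per 100 PY, which passes. With 3 events: 8.77/800 = 1.10, which fails.
- Expected events: 800 × 0.0015 = 1.2. P(at most 2) = e^(-1.2) × (1 + 1.2 + 0.72) = 0.880. The 88% is reproduced, as are 72% and 95% for N = 175 and 225.
- Two events continue to pass down to about 720 PY (3.6 years on average for 200 patients). At 700 PY the probability is 72%.

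**2. Recorded follow-up of the last entrant** = extraction date − lag − index date, over all dates within Q4 2026 and Q4 2030:

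| Lag | Same point in both quarters | Range |
|---|---|---|
| None | 4.00 y | 3.75-4.25 |
| 3 months | 3.75 y | 3.50-4.00 |
| 6 months | 3.50 y | 3.25-3.75 |

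With a 6-month lag no pair of dates reaches 4 years.

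**3. How many source patients.** Of 5307 moderate patients in Table 7, WBDR holds 2987 (56%), FranceCoag 940 (18%), UKNHD 836 (16%) and ATHNdataset 15. HemoNED and CBDR hold 230 + 299 = 529 (10%). These are all moderate patients, not emicizumab users, whose split by registry is not given.

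**4. Effect at the final analysis.** Assumptions: uniform entry, ending mid-Q4 2026 (2026.875); extraction mid-Q4 2030 (2030.875); 5-year cap; 6-month lag in every registry; no other censoring.
- Entry from 2023.06 (the EU decision of 23 January 2023), width 3.815 years. Full PY are proportional to 2.815 × 5 + 1.0 × 4.5 = 18.575; recorded PY to 2.315 × 5 + 1.5 × 4.25 = 17.95. Share without recorded events: 1 − 17.95/18.575 = 3.4%. Mean recorded follow-up: 17.95/3.815 = 4.7 years. Under 4 years: 0.5/3.815 = 13%.
- Entry from 2025.0, width 1.875 years. Full 8.875, recorded 8.25. Share 7.0%, mean 4.4 years, under 4 years 0.5/1.875 = 27%.
- A true rate of 0.15 would read as about 0.145 to 0.139 per 100 PY.

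**5. Effect at the interims.** Assumptions: uniform entry 2023.06 to 2027.0, 6-month lag, no event of the last 6 months recorded.
- Interim 1 (extraction 2025.4): 1 − (1.84/2.34)² = 38%.
- Interim 2 (extraction 2027.4): full 3.94 × 2.37 = 9.34; recorded 3.84²/2 = 7.37; share 21%.
- Final (2031.0) on the same basis: 1 − 18.575/19.2 = 3%.
- If patients who start within the lag window are themselves not yet recorded, the interim shares are about 35% and 21%.
- The shares depend on the entry pattern. Uniform entry from January 2024 would give 1 − (0.9/1.4)² = 59% and 1 − 4.205/5.7 = 26%.

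**The case against.** **The bias needs a rule that the protocol does not state outright.** Section 8.2.1 can be read as a data-content date rather than the day of extraction, and end of observation in 8.2.5 is an open list that could cover the last date on which a registry observed the patient. A registry-specific cut-off could also sit in the SAP, which is not at hand. This stands, and it makes the bias conditional. It does not rescue the minimum: no SAP rule can supply 4 recorded years when the extraction precedes the recording. If the end of study is a data-content date, the anticipated Q4 2030 does not fit a registry that is 6 months behind.

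**The shortfall is confined.** It touches only entrants after about mid-2026 in lagged registries. Participation is subject to contracting, the dates are approximate, and 8.1 lets study length vary by country. This stands as a limit on scope. A reader might infer that the study as a whole fails its 4-year minimum; the documents do not support that.

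**The primary precision is safe.** A reader might also infer that 3.5 years brings the 88% down to 72%. That would require every patient to average 3.5 years. The 88% assumes an average, earlier entrants can contribute up to 5 years, and mean recorded follow-up is 4.4-4.7 years before other censoring even with a 6-month lag everywhere. This stands in full.

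**The interim percentages apply to very few events.** With 200 entrants over the entry period and 0.15 per 100 PY, the whole cohort would yield about 139 PY and 0.2 expected events at interim 1, and about 474 PY and 0.7 at interim 2. For thromboembolic events this is fair. The same denominator also serves the serious adverse event rate, to which the same percentage would apply.

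**Conclusion.** The concern holds in a limited form. The schedule allows nothing for registry lag, so the stated 4-year minimum is wrong for late entrants in registries that run months behind: about 3.5 years (3.25-3.75) for the last entrants at a 6-month lag, 3.50-4.00 at 3 months, and unknown for FranceCoag. This follows from the protocol's own dates and Table 7.

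The downward bias is conditional on counting person-time to the common end date, which is the literal reading of 8.2.1 and 8.2.4. Its size is at most about 3-7% at the final analysis with a 6-month lag everywhere, for uniform entry starting between January 2023 and 2025. In a 6-month-lag registry it is at most about 38% and 21% at the two interims, for uniform entry from January 2023. These are ceilings because they assume that nothing from the last 6 months has been recorded.

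The sample size justification is unaffected. The point is worth correcting because a stated figure cannot be met and a safety rate could be understated for want of one sentence.

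**What to change.** 1. In 8.2.1 and 8.2.4, and in the specification of the common data model, end both events and person-time in each registry at its own data-complete date (extraction date minus that registry's lag). Apply this at every extraction, including the two interims.
2. Obtain FranceCoag's lag and enter it in Table 7.
3. Restate the minimum potential follow-up as about 3.5 years in registries with a 6-month lag, and align the synopsis, 8.1, 8.2.2 and 8.2.4.

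The cost is slightly fewer person-years and a less favourable stated minimum. Under the assumptions of step 4, 200 patients would give about 941 rather than 974 PY (entry from January 2023), or 880 rather than 947 (entry from 2025).

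Closing entry 6 months earlier is not advised. Under uniform entry it would lose 0.5/3.94 = 13% of entrants, about 202 down to 176, and Table 9 gives 72% for N = 175 at a 4-year average, although longer mean follow-up might offset part of this. Moving the last extraction 6 months later would put it in Q2 2031, the quarter of the final report, so that date would have to move too.

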8.2.3. Index date

The index date will be the date of emicizumab treatment initiation for each patient during the cohort entry period.

8.2.4. Follow-up Period

The study will allow for a minimum of 4 years of follow-up after the index date. The follow-up period will be the time period from index date (first emicizumab initiation) until, **Hemlibra—F. Hoffmann-La Roche Ltd** Protocol BO44691, Version 2.0

the end of the study period (anticipated Q4 2030), a maximum of 5 years of follow-up, or censoring.

8.2.5. Censoring

Patients will be followed until the end of study period or when meeting any of the following censoring criteria, the reason for censoring will be described, whichever occurs first:

- Death
- End of observation, e.g., due to loss to follow-up, emigration, or disenrollment from the registry
- Discontinuation of emicizumab treatment (as defined in the exposure section 8.3.2.2.)

8.2.6. Study Populations

HA patients that are naïve users of emicizumab will be selected based on the eligibility criteria presented below.

8.2.6.1. Inclusion Criteria

Patients must have met the following diagnostic criteria to be included in the study:

- Diagnosis of congenital HA.
- Moderate disease classification $(1\% \le FVIII \le 5\%)$.
- Severe bleeding phenotype, defined as the patient previously having had spontaneous bleedings and for whom prophylaxis is required to prevent such bleeding or other life-threatening complications per physicians opinion or as otherwise noted in the data source (Srivastava et al., 2020). Severe bleeding phenotype will be captured using the following criteria:
 - Ongoing or previous prophylactic treatment with clotting FVIII infusions (Carcao et al., 2020) during the 12 months prior to the index date.
 Or:
 - Spontaneous bleeding, defined as a bleeding that was not caused by trauma or a medical procedure at any time in the past prior to the index date.

Or:

• An annualised bleeding rate (ABR) of \geq 2 events/year in the 12 months prior to the index date.

Based on previous studies on bleeding phenotypes among moderate patients with haemophilia where ABR≥2 is above the 3rd ABR quartile (Kloosterman et al., 2022) or at the median and above (den Uijl et al., 2014).

Due to the variability of reporting in the data sources, the exact operational definition of the severe bleeding phenotype will vary between data sources. Table 1 shows the different criteria that can be fulfilled in each specific database.

Hemlibra—F. Hoffmann-La Roche Ltd

Protocol BO44691, Version

Data source	Country	Spontaneous bleeding prior to index date	Prophylactic treatment 12 months prior to index date	Annualised bleeding rate 12 months prior to index date
UKNHD	UK	Low	Low	Derived (number of new bleeding episodes at follow-up)
FranceCoag	France	Good	Good	Derived (bleeding events)
HemoNED	Netherlands	Captured	Captured	Derived (date/time of bleed, cause, location, and severity)
ATHN dataset	US	Not collected	Good*	Derived (bleed events)*
WBDR	Multi-country	Good	Good	Derived (total number of bleeds at baseline and at follow-up visits)
CBDR	Canada	Collected	Good	Derived (total number of bleeds)

Table 1. Applicable criteria for severe bleeding phenotype in the considered data sources.

*Bleed events not specified as traumatic or spontaneous.

UKNHD, UK National Haemophilia Database; **UK**, United Kingdom; **ATHNdataset**, American Thrombosis and Hemostasis Network; **US**; United States; **WBDR**, World Bleeding Disorders Registry; **CBDR**, Canadian Bleeding Disorders Registry.

Information from feasibility questionnaire or data dictionary: Good = >70% patients included in the disease registries have the required variable, Moderate = 40 - 70% patients with variable, Low <40% patients with variable, Captured = Not disclosed, Not collected = No patients with variable.

The above-mentioned inclusion criteria will ensure that the patient is eligible for the extended indication of emicizumab.

In addition, the patient will have to fulfil the following criteria:

- Initiation of emicizumab treatment during the cohort entry period.
- Information on previous HA outcomes and HA treatments approximately 12 months prior to the index date. In case HA diagnosis occurred within 12 months of the index date, the required lookback period will be shortened to time from HA diagnosis to index date. Anamnestic information capturing historic events but entered in the

Hemlibra—F. Hoffmann-La Roche Ltd

Protocol BO44691, Version 2.0

registry database less than 12 months before the index date will be considered as long as they were recorded prior to the index date.

- Information on risk factors of TE events (e.g., medical comorbidities, treatments and demographic characteristics) approximately 12 months prior to the index date. If the patient is below 1 year of age, the lookback period will be shortened to birth until index date. Anamnestic information capturing historic events but entered in the registry database less than 12 months before the index date will be considered as long as they were recorded prior to the index date.
- Signed the informed consent form where required by local regulations.

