8.7.2. Planned Analyses

For the analysis of the primary objective and secondary objectives 1, 2, and 3 the overall crude and crude stratified IRs will be calculated. The person-time of each patient will be based on the follow-up and censoring criteria presented in section 8.2.4. and 8.2.5.

For the calculation of crude IRs, the denominator will be the pooled person-time of all the patients within the cohort. The patient time-at-risk will be calculated from index date until the date of an incident event or censoring, whichever occurs first. All first events occurring during follow-up period will be counted in the total number of events. Crude IRs will be presented per 100 PY with 95% CI.

For the primary objective, the numerator will be the number of first TE events of all patients within the cohort. For secondary objectives 1, 2, 3 the numerator will be the number of first occurrences of any SAE; TMA events or serious systemic hypersensitivity reactions, including anaphylaxis; respectively.

For the analysis of secondary objective 4, calculation of crude stratified IRs of 1st TE events will be done. The events will be counted for each category/stratum of relevant pre-defined risk factors (see section 8.3.2.4. for a listing of considered risk factors). More details on the risk factor based tabulations will be presented in SAP.

For analysis of secondary objective 5, characteristics of TE events, SAEs, TMA, and serious systemic hypersensitivity reactions, including anaphylaxis (e.g., diagnosis and symptoms), will be tabulated. In addition, time to 1st TE event; time to 1st TMA event; time to 1st serious systemic hypersensitivity reactions, including anaphylaxis; and time to any 1st SAE event will be described by Kaplan-Meier curves.

For analysis of secondary objective 6, calculation of crude IR and crude incidence proportion of TE, TMA events, SAEs and serious systemic hypersensitivity reactions, **Hemlibra—F. Hoffmann-La Roche Ltd** Protocol BO44691, Version 2.0

including anaphylaxis, will be calculated and tabulated for FVIII prophylaxis use (yes/no) prior to emicizumab treatment.

Patient demographic and clinical characteristics will also be tabulated in relation to the AEs (TE events, SAEs, TMA events and serious systemic hypersensitivity reactions, including anaphylaxis) and in total.

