9. PROTECTION OF HUMAN PATIENTS

9.1. INFORMED CONSENT

The MAH will identify whether a new informed consent form is needed for using the data from the registries. For example, in some cases, additional patient informed consent forms or information letters indicating that the data will be transferred to another organisation for analysis may be required and will have to be obtained from individual patients depending on the rules and regulations setup by the data source or local authorities.

In addition to ensuring whether informed consent is needed certain precautions will be taken, including:

- Ensuring data are anonymised / pseudonymised
- Ensuring final analysis data are anonymised / pseudonymised
- Ensuring possibility of linkage back to individual identified patients is impossible or tightly controlled
- Obtaining ethical committee approval for use of data as proposed (e.g., the review of and extraction of information from individual medical charts) records for the proposed use ahead of study initiation

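### Where new signed consent is needed, it is not tied to the index date although person-time is; consent signed later would bias the TE and SAE rates downward for patients starting after protocol approval

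*Protocol*

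**What the plan says.** **Entry.** Section 8.2.6.1 lists as an inclusion criterion: "Signed the informed consent form where required by local regulations". No date is attached. The bleeding-phenotype and lookback criteria in the same section are all anchored to the index date.

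**New consent is possible.** Section 9.1 expects that for certain sources "additional patient informed consent forms or information letters indicating that the data will be transferred to another organisation for analysis may be required". On how these are collected, the section says that they "will have to be obtained from individual patients depending on the rules and regulations setup by the data source or local authorities". It names no registry.

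**Clock.** Section 8.2.3: "The index date will be the date of emicizumab treatment initiation for each patient during the cohort entry period". Section 8.7.2: "The patient time-at-risk will be calculated from index date until the date of an incident event or censoring, whichever occurs first". On the numerator it adds: "All first events occurring during follow-up period will be counted in the total number of events". No delayed entry is described.

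**Existing limit.** Section 8.2.2: "Patients who initiated emicizumab before protocol approval will be considered for inclusion as long as re-consent is not required by the data sources". No equivalent rule covers patients who start after protocol approval.

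**Exits.** Section 8.2.5 censors at death, at treatment discontinuation and at "End of observation, e.g., due to loss to follow-up, emigration, or disenrollment from the registry".

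The selection- and information-bias text in section 8.9 and the four sensitivity analyses in Table 10 do not mention survival to consent. Sensitivity analysis 1 changes censoring at the end of treatment, not entry. Table 2 lists the inclusion variables, and neither consent nor its date is among them.

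**The concern.** Eligibility that can be completed after time zero, combined with person-time counted from time zero, is the usual source of immortal time. Take a patient who starts emicizumab after protocol approval in a registry where new signed consent is needed. If a fatal TE event comes before the signature, the criterion as written cannot be met, and neither the event nor the time is counted. A patient who survives and signs later brings in the whole interval from index to signature, during which death was impossible by selection.

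The error runs towards apparent safety, the unwelcome direction in a post-authorisation safety study whose primary result is a crude rate. Few events are expected, so individual fatal cases carry weight.

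**Working it through.** **1. The plan's own figure.** Inputs from section 8.5.2: 200 patients × 4 years = 800 PY; expected rate 0.15 per 100 PY; threshold 1 per 100 PY; 95% Clopper-Pearson interval.
- Expected events: 800 × 0.0015 = 1.2.
- The upper limit is 0.90 per 100 PY with 2 events and 1.09 with 3, so at most 2 events are allowed.
- P(X ≤ 2 | n = 800, p = 0.0015) = 0.8796, which reproduces the stated 88%. The other five cells of Table 9 also reproduce. The consent question does not alter these design figures.

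**2. Who is exposed to the bias.** All of the following must hold: the source requires new signed consent; the patient started after protocol approval (section 8.2.2 already removes earlier starters who need re-consent); the signature follows the index date; and the event itself prevents the signature.

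**3. Size, on assumed inputs.** The protocol gives none of these three:
- q = share of patients who consent after index
- L = lag from index to consent, in years
- f = share of pre-consent TE events that prevent consent, through death or exit because of the event

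With 4 years of follow-up and a constant hazard:

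observed rate ≈ 0.15 × (1 − q × f × L / 4)

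| q | L (years) | f | Reduction q·f·L/4 | Observed rate per 100 PY |
|---|---|---|---|---|
| any | any | 0 | 0 | 0.150 |
| 0.25 | 0.5 | 0.3 | 0.9% | 0.149 |
| 1 | 1 | 0.1 | 2.5% | 0.146 |
| 1 | 1 | 0.3 | 7.5% | 0.139 |
| 1 | 1 | 1 | 25% | 0.1125 |
| 1 | 2 | 1 | 50% | 0.075 |

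The last two rows are extremes in which every pre-consent TE event prevents consent.

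Expected TE events lost are 1.2 × q·f·L/4: about 0.01 in the second row, 1.2 × 0.075 = 0.09 in the fourth and 0.3 in the fifth.

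**4. Simulation check** (10 million patients, q = 1, L = 1):
- f = 0.3: observed 0.138 against a true 0.149.
- f = 1: observed 0.113 against a true 0.151.
- Exits at 2% per year unrelated to TE, f = 0: 0.150 against 0.150, so no bias.

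**5. What is not lost.** A non-fatal TE event or SAE before consent is counted once the patient signs, because section 8.7.2 counts all first events in follow-up. An exit unrelated to the event removes numerator and denominator together. The documents give no expected SAE rate, so no figure is put on the SAE bias, but the mechanism is the same.

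**The case against.** The case against is substantial, and most of it limits the point without removing it.

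- **The gap is conditional.** Consent applies only where local rules require it, section 9.1 also allows information letters in place of consent forms, and no considered registry is said to need new consent. This stands: the bias is possible, not established.
- **Existing rules narrow it.** Section 8.2.2 removes the patients with the longest possible gap. The lookback criteria require information recorded before the index date, so registry enrolment, with any consent given at enrolment, should mostly precede index. This also stands. What remains is study-specific consent signed late by later starters.
- **It could be left to the SAP.** This stands only in part. The protocol itself fixes both the undated criterion and the start of the clock.

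Three stronger readings are tempting, and the documents do not support them.

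- *Everyone who leaves before signing lowers the rate.* Only fatal events and exits caused by an event do so.
- *A large share of person-time is immortal, so the bias is large.* Suppose entry is uniform over 2024–2026 and consent is collected only at the Q2 2025 and Q2 2027 extractions. The mean gap is then (0.75 + 1.25)/2 = 1.0 year, or 21% of a mean follow-up of 4.83 years. Nothing links consent to extraction, and section 8.1 says extraction is annual. Annual rounds give (1.5 × 0.75 + 1.0 × 0.5 + 0.5 × 0.75)/3 = 0.67 year, or 14%. Either way, immortal share is not rate bias.
- *One missing event would change the conclusion, so the result is unreliable.* A single loss could move 3 events to 2 and so cross the threshold, but the expected loss is 0.09 events even with q = 1, L = 1 and f = 0.3.

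**Conclusion.** The point holds in a limited form. For patients who start after protocol approval in a source that requires new signed consent, the protocol does not ask for consent by the index date and yet counts person-time from it. Wherever the signature comes later, fatal events and event-caused exits before it are lost, and the crude TE and SAE rates are biased downward. No planned analysis would show this.

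The size cannot be derived from the documents. Under the assumed values above, the TE rate moves from 0.150 to 0.149 or 0.139 per 100 PY. A large effect needs wide consent requirements, long lags and a high share of events that prevent consent, all together. The result rests on a constant hazard, on 4 years of follow-up, and on an unsigned patient being left out even after death, as the criterion reads. The 88% and Table 9 stand as stated.

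**What to change.** 1. In sections 8.2.6.1 and 8.7.2, choose one of two rules for sources that require new consent. **Either** require consent to be in place by the index date, **or** record the consent date in the common data model and add an analysis that counts events and person-time from the later of index and consent, reported beside the planned index-based rate. Time since index should remain the scale of the Kaplan-Meier curves.
2. By registry, report the lag from index to consent and, where local rules allow, the number of otherwise eligible initiators who died or left before consenting.
3. Name this bias in section 8.9.

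**Cost.** One rule and one date variable. The variable should be specified before the first extraction. Table 7 shows no patient-level access for WBDR and CBDR, which hold 2987 + 299 = 3286 of the 5307 moderate patients (62%). If either needs new consent, a date missing from the specification could not be recovered from the aggregates.

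**Downside.** Delayed entry drops pre-consent person-time, about N × q × L: 200 × 0.25 × 0.5 = 25 PY of 800 in the milder scenario, and 200 × 1 × 1 = 200 PY if all patients sign a year late. It also discards early non-fatal events that the present plan counts. With about 1.2 TE events expected, it should be an added analysis and not a replacement.
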